8. SAFETY AND ADVERSE EVENTS

8.1 Event Definitions

Adverse event reporting will be as per the NCI criteria and the MDACC Leukemia Specific Adverse Event Recording and Reporting Guidelines and the study will be monitored for compliance by the IND office

The descriptions and grading scales found in the revised NCI Common Terminology Criteria for Adverse Events (CTCAE) most current version (version 4.0) will be utilized for adverse event reporting. (http://ctep.cancer.gov/reporting/ctc.html).

Adverse drug reaction is a response to a drug which is noxious and unintended and which occurs at doses normally used in man for prophylaxis, diagnosis, or therapy of disease or for the modification of physiologic function.

All "suspected adverse reactions" (as defined in 21 CFR 312.32(a)) will be captured in the case report forms. For abnormal chemical values grade 3 or 4, the apogee will be reported per course in the CRF.

Assessing causal connections between agents and disease is fundamental to the understanding of adverse drug reactions. In general, a drug may be considered a contributory cause of an adverse event if, had the drug not been administered, 1) the event would not have happened at all, 2) the event would have occurred later than it actually did, or 3) the event would have been less severe.

The Investigator or physician designee is responsible for verifying and providing source documentation for all adverse events and assigning the attribution for each event for all subjects enrolled on the trial. Protocol specific data and adverse events will be entered into PDMS/CORe, the electronic case report form for this protocol.

Confidential

8.2 Serious Adverse Event Definition

An adverse event or suspected adverse reaction is considered "serious" if, in the view of either the investigator or the sponsor, it results in any of the following outcomes:

- Death
- A life-threatening adverse drug experience any adverse experience that places the patient, in the view of the initial reporter, at immediate risk of death from the adverse experience as it occurred. It does not include an adverse experience that, had it occurred in a more severe form, might have caused death.
- Inpatient hospitalization or prolongation of existing hospitalization
- A persistent or significant incapacity or substantial disruption of the ability to conduct normal life functions.
- A congenital anomaly/birth defect

Important medical events that may not result in death, be life-threatening, or require hospitalization may be considered a serious adverse drug experience when, based upon appropriate medical judgment, they may jeopardize the patient or subject and may require medical or surgical intervention to prevent one of the outcomes listed in this definition. Examples of such medical events include allergic bronchospasm requiring intensive treatment in an emergency room or at home, blood dyscrasias or convulsions that do not result in inpatient hospitalization, or the development of drug dependency or drug abuse (21 CFR 312.32).

Important medical events as defined above may also be considered serious adverse events. Any important medical event can and should be reported as an SAE if deemed appropriate by the Principal Investigator or the IND Sponsor, IND office.

All events occurring during the conduct of a protocol and meeting the definition of a SAE must be reported to the IRB in accordance with the timeframes and procedures outlined in "The University of Texas M. D. Anderson Cancer Center Institutional Review Board Policy for Investigators on Reporting Unanticipated Adverse Events for Drugs and Devices". Unless stated otherwise in the protocol, all SAEs, expected or unexpected, must be reported to the IND Office, regardless of attribution (within 5 working days of knowledge of the event).

Only unexpected AEs will be recorded in the Case Report Form (CRF). The Principal Investigator will sign and date the PDMS/CORe Case Report Form toxicity pages per each patient at the completion of each course. Following signature, the Case Report Form will be

used as source documentation for the adverse events for attribution.

All life-threatening or fatal events, that are unexpected, and related to the study drug, must have a written report submitted within 24 hours (next working day) of knowledge of the event to the Safety Project Manager in the IND Office.

Unless otherwise noted, the electronic SAE application (eSAE) will be utilized for safety reporting to the IND Office and MDACC IRB.

Serious adverse events will be captured from the time of the first protocol-specific intervention, until 30 days after the last dose of drug unless the participant withdraws consent. Serious adverse events must be followed until clinical recovery is complete and laboratory tests have returned to baseline, progression of the event has stabilized, or there has been acceptable resolution of the event.

Additionally, any serious adverse events that occur after the 30 day time period that are related to the study treatment must be reported to the IND Office. This may include the development of a secondary malignancy.

The following SAEs are not subject to expedited reporting, but would still be included in the annual report via the SAE log.

Disease progression leading to death, life-threating AE, hospitalization or prolongation of hospitalization, or disability

Reporting to FDA:

Serious adverse events will be forwarded to FDA by the IND Sponsor (Safety Project Manager IND Office) according to 21 CFR 312.32

It is the responsibility of the PI and the research team to ensure serious adverse events are reported according to the Code of Federal Regulations, Good Clinical Practices, the protocol guidelines, the sponsor's guidelines, and Institutional Review Board policy.

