8.4 SAE Reporting to Study Supporter (Millenium)

AEs may be spontaneously reported by the patient and/or in response to an open question from study personnel or revealed by observation, physical examination, or other diagnostic procedures. Any clinically relevant deterioration in laboratory assessments or other clinical finding is considered an AE. When possible, signs and symptoms indicating a common underlying pathology should be noted as one comprehensive event. For serious AEs, the investigator must determine both the intensity of the event and the relationship of the event to study drug administration. All SAEs, regardless of attribution, and adverse events related to study drug, will be entered in the CRF.

AEs which are serious must be reported to Millennium Pharmacovigilance (or designee) from the first dose of study drug through 30 days after administration of the last dost of ixazomib. Any SAE that occurs at any time after completion of ixazomib treatment or after the designated follow-up period that the principal investigator and/or sub-investigator considers to be related to any study drug must be reported to Millennium Pharmacovigilance (or designee). In addition, new primary malignancies that occur during the follow-up periods must be reported, regardless of seriousness or causality to study regimen, for a **Confidential** 48 V8 11May15 minimum of three years after the last dose of the investigational product, starting from the first dose of study drug. All new cases of primary malignancy must be reported to Millennium Pharmacovigilance (or designee).

Planned hospital admissions or surgical procedures for an illness or disease that existed before the patient was enrolled in the trial are not to be considered AEs unless the condition deteriorated in an unexpected manner during the trial (e.g., surgery was performed earlier or later than planned). All SAEs should be monitored until they are resolved or are clearly determined to be due to a patient's stable or chronic condition or intercurrent illness(es).

Since this is an investigator-initiated study, the principal investigator [name], is responsible for reporting serious adverse events (SAEs) to any regulatory agency and to the investigator's EC or IRB.

Regardless of expectedness or causality, all SAEs must also be reported in English to Millennium Pharmacovigilance (or designee):

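### Section 8.2 limits the CRF to unexpected adverse events, against 8.1 and 8.4; if 8.2 is followed, the all-adverse-event safety endpoint in 3.2 is under-reported

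*Combined protocol and SAP*

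**What the plan says.** Four instructions in Section 8 set what enters the CRF, and a fifth covers chemistry values.

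- 8.1, first rule: "All 'suspected adverse reactions' (as defined in 21 CFR 312.32(a)) will be captured in the case report forms".
- 8.1, second rule: "Protocol specific data and adverse events will be entered into PDMS/CORe, the electronic case report form for this protocol". It has no qualifier by seriousness, relatedness or expectedness.
- 8.1, chemistry values: "For abnormal chemical values grade 3 or 4, the apogee will be reported per course in the CRF".
- 8.2: "Only unexpected AEs will be recorded in the Case Report Form (CRF". It has no qualifier by seriousness or relatedness.
- 8.4: "All SAEs, regardless of attribution, and adverse events related to study drug, will be entered in the CRF".

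Two other parts of the plan depend on these data. Section 3.2 defines the safety endpoint as the incidence and severity of every adverse event, graded by CTCAE. Section 7.1.5 reports toxicity by type, frequency and severity, and tabulates the highest grade per patient per course for selected adverse events and laboratory measurements.

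Section 8.1 opens by referring adverse event reporting to the NCI criteria and to the institution's leukemia-specific recording and reporting guideline. The content of that guideline is not in the supplied documents.

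**The concern.** The events that 8.2 removes are those already known for the drug. Section 6.7 associates ixazomib with thrombocytopenia, diarrhea, fatigue, nausea, vomiting and rash. A single-arm phase II study in a new population needs to describe exactly these reactions. A CRF restricted to unexpected events would hold the surprises and omit the common, known toxicity, while 3.2 promises incidence and severity for everything.

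There is a second consequence for attribution. Section 8.2 goes on to say that, once signed, the CRF serves as the source document for attributing adverse events. An event that never enters the CRF has no attribution recorded there, although any tabulation of related toxicity needs one.

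**Working it through.** The point rests on no stated figure, so the check sets the recording rules side by side. Each row is a class of event. *In* means that the rule requires it in the CRF, *out* means that the rule excludes it, and *silent* means that the rule does not reach it.

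| Event class | 8.1 suspected reactions | 8.1 PDMS/CORe | 8.2 | 8.4 | Needed for 3.2 |
|---|---|---|---|---|---|
| Drug-related, non-serious, unexpected | in | in | in | in | yes |
| Drug-related, non-serious, expected | in | in | **out** | in | yes |
| Drug-related SAE, expected | in | in | **out** | in | yes |
| Unrelated SAE, expected | silent | in | **out** | in | yes |
| Unrelated, non-serious, unexpected | silent | in | in | silent | yes |
| Unrelated, non-serious, expected | silent | in | **out** | silent | yes |

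Four things follow.

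1. **The conflict is direct.** In rows 2 and 3, both rules of 8.1 and the rule of 8.4 require the event and 8.2 excludes it. Row 4 conflicts with 8.4 and with the second rule of 8.1. Staff cannot obey all the sections.
2. **Read literally, 8.2 excludes expected SAEs from the CRF as well as non-serious events.** They are not lost to safety reporting. The same section states that "all SAEs, expected or unexpected, must be reported to the IND Office, regardless of attribution", and 8.4 sends all SAEs to the study supporter regardless of expectedness or causality.
3. **8.2 is not the only rule narrower than the endpoint.** The last two rows show that the first rule of 8.1 and the rule of 8.4 do not reach unrelated non-serious events. Only the PDMS/CORe sentence in 8.1 matches 3.2 in full. Deleting the 8.2 sentence removes the contradiction but still leaves several capture scopes.
4. **The SAE heading does not rescue the sentence.** It speaks of adverse events, and the sentence after it concerns the CRF toxicity pages. Read as SAE-only, it would still contradict 8.4.

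**Size.** Table 1-2 pools 201 patients on single-agent oral ixazomib. It reports nausea in 106/201 (53%), fatigue in 103/201 (51%), diarrhea in 88/201 (44%), vomiting in 77/201 (38%) and thrombocytopenia in 68/201 (34%). This shows that the reactions in 6.7 are common. It does not size the gap: the figures come from other malignancies and several doses, and they do not separate serious from non-serious or expected from unexpected. The documents give no share of expected events for this trial, so no under-reporting rate can be derived.

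**What would still be captured if 8.2 were followed.** SAEs go through their own routes. The grade 3 or 4 chemistry rule in 8.1 carries no expectedness limit. The study calendar requires blood counts, so cytopenias can be graded from laboratory data. Table 6-3 requires related grade 3 non-hematologic events to be identified for dose action. None of these puts expected, non-serious nausea, diarrhea, fatigue or rash into the CRF.

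**The case against.** The strongest defense is that 8.1 does name a governing document, the institutional guideline, and that it may say exactly what goes in the CRF. That stands in part: whether any event would actually be lost depends on a text that is not supplied. It does not remove the contradiction, because the protocol itself still gives opposing instructions and says nothing on how to resolve them.

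A second defense is that nothing is lost from the record, since the investigator is "responsible for verifying and providing source documentation for all adverse events and assigning the attribution for each event". This also stands in part. The gap lies in the CRF data that would be tabulated, and not necessarily in the medical record.

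A third is that the supplied text does not define expectedness, so treating the reactions in 6.7 as expected is an inference. That is fair, and the point says probably for this reason.

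A reader might go further and infer that the toxicity stopping rule in 7.1.5 is compromised. The documents do not support that. The rule counts clinically significant treatment-related grade 3 or higher toxicity with no expectedness limit, but 7.1.5 does not say where the count comes from. An under-count would need 8.2 to be followed, the CRF to feed the count, and the patient's qualifying events to be caught by no other route. Any figure for lost stopping probability would reflect an assumed miss rate and not the protocol.

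A reader might also infer that monitoring lags because the investigator signs the "toxicity pages per each patient at the completion of each course". That sentence ties the signature to the end of the course. It does not say that events are entered only then, or that monitoring waits for the signature.

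**Conclusion.** The contradiction is certain: 8.2 cannot be followed together with 8.1 and 8.4, and no supplied passage resolves it. If 8.2 is followed, the CRF omits expected events, and the 3.2 endpoint and the adverse event part of the 7.1.5 tabulation are under-reported. The laboratory part of that tabulation is better protected, because protocol-required counts and chemistries exist independently.

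The size is unknown. The conclusion about consequences rests on two assumptions: that staff apply the 8.2 sentence as written, and that the known ixazomib reactions count as expected. The unseen guideline could change what happens in practice.

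The primary RFS analysis is not affected, because its events are relapse and death. An effect on the stopping rule is possible but not established. This should be fixed: the defect bears on a stated safety endpoint, and the repair is small.

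**What to change.** - Delete the 8.2 sentence that limits the CRF to unexpected adverse events.
- State one capture rule: all adverse events are recorded in the CRF with grade and attribution, regardless of expectedness, seriousness or relatedness.
- Align 8.1 and 8.4 with that rule and with 3.2. Deletion alone would leave the first rule of 8.1 and the rule of 8.4 silent on unrelated non-serious events.
- Check the institutional guideline named in 8.1 against the same rule. If it is narrower, say in the protocol that the protocol rule governs for this study.
- Optionally, add to 7.1.5 that the toxicity count includes qualifying events whether expected or not.

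The cost is one deleted sentence, a few clarifying ones, and somewhat more CRF entry. The study calendar already has adverse events assessed at every scheduled visit, so no new assessment is needed. No dose or clinical rule changes.

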8.3 Procedures for Reporting Drug Exposure During Pregnancy and Birth Events

If a female subject or partner of a male subject becomes pregnant during the study dosing period or within 3 months from the discontinuation of dosing, the investigator should report the information to the study supporter as if it is an SAE. The PI must immediately fax a completed Pregnancy Form to the Millennium Department of Pharmacovigilance or

Confidential

designee (see Section 8.3). The expected date of delivery or expected date of the end of the pregnancy, last menstruation, estimated fertility date, pregnancy result and neonatal data etc., should be included in this information. The investigator will follow the medical status of the mother, as well as the fetus, as if the pregnancy is an SAE.

When the outcome of the pregnancy falls under the criteria for SAEs [spontaneous abortion, induced abortion, stillbirth, death of newborn, congenital anomaly (including anomaly in a miscarried fetus)], the investigator should respond in accordance with the report procedure for SAEs. Additional information regarding the outcome of a pregnancy (which is categorized as an SAE) is mentioned below.

- "Spontaneous abortion" includes abortion and missed abortion.
- Death of an infant within 28 days after birth should be reported as an SAE regardless of its relationship with the study drug.
- Any infant death after 28 days that the Investigator suspects is related to the in utero exposure to the IP should also be reported to MPI/PPD Drug Safety immediately by facsimile, or other appropriate method, within 24 hours of the Investigator's knowledge of the event using the SAE Report Form, or approved equivalent form.
- In the case of a delivery of a living newborn, the "normality" of the infant is evaluated at the birth.
- "Normality" of the miscarried fetus is evaluated by visual examination unless test results which indicate a congenital anomaly are obtained prior to miscarriage.

8.4 SAE Reporting to Study Supporter (Millenium)

AEs may be spontaneously reported by the patient and/or in response to an open question from study personnel or revealed by observation, physical examination, or other diagnostic procedures. Any clinically relevant deterioration in laboratory assessments or other clinical finding is considered an AE. When possible, signs and symptoms indicating a common underlying pathology should be noted as one comprehensive event. For serious AEs, the investigator must determine both the intensity of the event and the relationship of the event to study drug administration. All SAEs, regardless of attribution, and adverse events related to study drug, will be entered in the CRF.

AEs which are serious must be reported to Millennium Pharmacovigilance (or designee) from the first dose of study drug through 30 days after administration of the last dost of ixazomib. Any SAE that occurs at any time after completion of ixazomib treatment or after the designated follow-up period that the principal investigator and/or sub-investigator considers to be related to any study drug must be reported to Millennium Pharmacovigilance (or designee). In addition, new primary malignancies that occur during the follow-up periods must be reported, regardless of seriousness or causality to study regimen, for a **Confidential** 48 V8 11May15 minimum of three years after the last dose of the investigational product, starting from the first dose of study drug. All new cases of primary malignancy must be reported to Millennium Pharmacovigilance (or designee).

Planned hospital admissions or surgical procedures for an illness or disease that existed before the patient was enrolled in the trial are not to be considered AEs unless the condition deteriorated in an unexpected manner during the trial (e.g., surgery was performed earlier or later than planned). All SAEs should be monitored until they are resolved or are clearly determined to be due to a patient's stable or chronic condition or intercurrent illness(es).

Since this is an investigator-initiated study, the principal investigator [name], is responsible for reporting serious adverse events (SAEs) to any regulatory agency and to the investigator's EC or IRB.

Regardless of expectedness or causality, all SAEs must also be reported in English to Millennium Pharmacovigilance (or designee):

Fatal and Life Threatening SAEs within 24 hours of the principle investigator's observation or awareness of the event

All other serious (non-fatal/non life threatening) events within 4 calendar days of the principle investigator's observation or awareness of the event

See below for contact information for the reporting of SAEs to Millennium Pharmacovigilance.

The PI must fax or email the SAE Form per the timelines above. A sample of an SAE Form will be provided.

The SAE report must include at minimum:

- Event term(s)
- Serious criteria
- Intensity of the event(s): The PI or sub-investigator's determination. Intensity for each SAE, including any lab abnormalities, will be determined by using the NCI CTCAE version specified in the protocol, as a guideline, whenever possible. The criteria are available online at http://ctep.cancer.gov/reporting/ctc.html.
- **Causality of the event(s):** PI's or sub-investigator's determination of the relationship of the event(s) to study drug administration.

Follow-up information on the SAE may be requested by Millennium.

Intensity for each SAE, including any lab abnormalities, will be determined by using the NCI CTCAE version used at your institution, as a guideline, whenever possible. The criteria are available online at http://ctep.cancer.gov/reporting/ctc.html.

In the event that this is a multisite study, the PIis responsible to ensure that the SAE reports are sent to Millennium Pharmacovigilance (or designee) from all sites participating in the study. Sub-investigators must report all SAEs to the PI so that the PI can meet his/her foregoing reporting obligations to the required regulatory agencies and to Millennium Pharmacovigilance, unless otherwise agreed between the PI and sub-investigator(s).

Relationship to all study drugs for each SAE will be determined by the investigator or subinvestigator by responding yes or no to the question: Is there a reasonable possibility that the AE is associated with the study drug(s)?

The PI must also provide Millennium Pharmacovigilance with a copy of all communications with applicable regulatory authorities related to the study product(s), as soon as possible but no later than 4 calendar days of such communication.

SAE and Pregnancy Reporting Contact Information

SAE and Pregnancy Reporting Contact Information

[contact] Email: [contact]

Suggested Reporting Form:

- SAE Report Form
- US FDA MedWatch 3500A:

http://www.fda.gov/Safety/MedWatch/HowToReport/DownloadForms/default.htm

• Any other form deemed appropriate by the PI

